4.5.8.1 Tissue Sample Prioritization

Analyses of samples will be prioritized as specified below. See [Table 4](#) for proposed analyses.

Pre- and Post-Treatment FFPE Biopsy Samples

1. Pathology analyses
2. PD-L1 IHC analysis
3. Multiplex IF analysis
4. Additional exploratory analyses

Pre- and Post-Treatment Fresh Frozen Biopsy Samples

1. RNA and DNA isolation for next generation sequencing
2. Additional exploratory analyses

Fresh Lymph Node Biopsy (if available)

1. Cellular IMMUNOME
2. Additional exploratory analyses

All other tissue samples (tumor, lymph node, bronchial brushings, adjacent normal lung) will be used for additional exploratory analyses.

4.6 PATIENT, TREATMENT, STUDY, AND SITE DISCONTINUATION

4.6.1 Patient Discontinuation

Patients have the right to voluntarily withdraw from the study at any time for any reason. In addition, the investigator has the right to withdraw a patient from the study at any time. Reasons for withdrawal from the study may include, but are not limited to, the following:

- Patient withdrawal of consent at any time
- Any medical condition that the investigator or Sponsor determines may jeopardize the patient's safety if he or she continues in the study
- Investigator or Sponsor determines it is in the best interest of the patient
- Patient non-compliance

Every effort should be made to obtain information on patients who withdraw from the study but do not withdraw consent. The primary reason for withdrawal from the study should be documented on the appropriate eCRF. However, patients will not be followed for any reason after consent has been withdrawn. Patients who withdraw from the study will not be replaced.

If a patient withdraws from the study, the study staff may use a public information source (e.g., county records) to obtain information about survival status.

4.6.2 Atezolizumab Treatment Discontinuation

Patients must discontinue neoadjuvant or adjuvant atezolizumab treatment if they experience any of the following:

- Pregnancy
- Radiographic disease progression and/or symptomatic deterioration attributed to disease progression as determined by the investigator after integrated assessment of radiographic data, biopsy results, and clinical status. Please note all radiographic images related to disease will be collected.
- Intolerable toxicity related to atezolizumab, including development of an irAE determined by the investigator to be unacceptable given the individual patient's potential response to therapy and severity of the event. May contact Medical Monitor and Sponsor for further guidance.
- Any medical condition that the investigator or Sponsor determines may jeopardize the patient's safety if he or she continues on atezolizumab
- Use of another non-protocol-specified anti-cancer therapy

The primary reason for atezolizumab discontinuation should be documented on the appropriate eCRF.

If patient prematurely discontinues neo-adjuvant treatment for any reason other than progressive disease (after Cycle 1 and before surgery), they may proceed with surgery as part of the study and enter surveillance. If patient discontinues treatment for any

reason after surgery, they should remain in Surveillance until they complete 2 years and then move to Survival Follow-up. Patients who discontinue atezolizumab prematurely will not be replaced.

4.6.3 Study and Site Discontinuation

The Sponsor has the right to terminate this study at any time. Reasons for terminating the study may include, but are not limited to, the following:

- The incidence or severity of adverse events in this or other studies indicates a potential health hazard to patients.
- Patient enrollment is unsatisfactory.

The Sponsor will notify the investigator if the Sponsor decides to discontinue the study.

The Sponsor has the right to close a site at any time. Reasons for closing a site may include, but are not limited to, the following:

- Excessively slow recruitment
- Poor protocol adherence
- Inaccurate or incomplete data recording
- Non-compliance with the International Conference on Harmonisation (ICH) guideline for Good Clinical Practice
- No study activity (i.e., all patients have completed the study and all obligations have been fulfilled)

5. ASSESSMENT OF SAFETY

5.1 SAFETY PLAN

Atezolizumab is approved in the United States for the treatment of locally advanced or metastatic UC. The safety plan for patients in this study is based on clinical experience with atezolizumab in completed and ongoing studies. The anticipated important safety risks for atezolizumab are outlined below.

Measures will be taken to ensure the safety of patients participating in this study, including the use of stringent inclusion and exclusion criteria and close monitoring of patients during the study. Administration of atezolizumab will be performed in a monitored setting in which there is immediate access to trained personnel and adequate equipment and medicine to manage potentially serious reactions. Guidelines for managing anticipated adverse events, including criteria for dosage modification and treatment interruption or discontinuation, are provided below. In addition, a pre-specified interim safety analysis will be conducted to evaluate the safety data during the study.

Patients with active infection are excluded from study participation. In the setting of a pandemic or epidemic, screening for active infections (including SARS-CoV-2) prior to and during study participation should be considered according to local or institutional

guidelines or guidelines of applicable professional societies (e.g., American Society of Clinical Oncology or European Society for Medical Oncology).

Severe SARS-CoV-2 infection appears to be associated with a CRS involving the inflammatory cytokines IL-6, IL-10, IL-2, and IFN- γ (Merad and Martin 2020). If a patient develops suspected CRS during the study, a differential diagnosis should include SARS-CoV-2 infection, which should be confirmed or refuted through assessment of exposure history, appropriate laboratory testing, and clinical or radiologic evaluations per investigator judgment. If a diagnosis of SARS-CoV-2 infection is confirmed, the disease should be managed as per local or institutional guidelines.

5.1.1 Risks Associated with Atezolizumab

Atezolizumab has been associated with risks such as the following: infusion-related reactions (IRRs) and immune-mediated hepatitis, pneumonitis, colitis, pancreatitis, diabetes mellitus, hypothyroidism, hyperthyroidism, adrenal insufficiency, hypophysitis, Guillain-Barré syndrome, myasthenic syndrome or myasthenia gravis, meningoencephalitis, myocarditis, nephritis, myositis, and severe cutaneous adverse reactions. Immune-mediated reactions may involve any organ system and may lead to hemophagocytic lymphohistiocytosis (HLH) and macrophage activation syndrome (MAS), which are considered to be potential risks for atezolizumab.

Refer to [Appendix 9](#) of the protocol and Section 6 of the Atezolizumab Investigator's Brochure for a detailed description of anticipated safety risks for atezolizumab.

5.1.2 Management of Patients Who Experience Specific Adverse Events

Guidelines for management of patients who experience specific adverse events associated with atezolizumab, including infusion-related reactions and immune-mediated events (e.g., myocarditis and pulmonary, hepatic, gastrointestinal, endocrine, ocular, pancreatic, dermatologic, neurologic, and renal events), are provided in the [Appendix 9](#).

5.1.2.1 Atezolizumab Dose Modification and Treatment Interruption

Atezolizumab dose modification is not allowed in the Neoadjuvant Atezolizumab Therapy Phase. The following rules apply: 1) if atezolizumab is interrupted during infusion due to reaction, but resumed, *the patient may proceed with all future study-related activities*, 2) if atezolizumab is held (e.g., treatment is delayed) after *the first dose* due to tolerability concerns, the Investigator may choose to discontinue *the patient from the study if medically indicated*, and 3) if the patient receives less than prescribed dose of atezolizumab (e.g., if infusion cannot be completed), patient continuation in the study will require Medical Monitor approval. If the patient does not discontinue from study, they may proceed as per protocol. Investigator may contact Medical Monitor for further guidance. If the patient discontinues treatment, they will enter Survival Follow-up, as specified in Section [4.6](#).

Atezolizumab dose modification is not allowed during Adjuvant Atezolizumab Therapy Phase. However, atezolizumab may be temporarily suspended in patients experiencing toxicity considered to be related to atezolizumab for up to 12 weeks after the last dose if they experience toxicity that require a dose to be withheld. If atezolizumab is withheld because of toxicity for > 12 weeks after the last dose, then the patient will be discontinued from atezolizumab treatment and will be followed for safety and efficacy as specified in Section 4.6. If a patient must be tapered off corticosteroids used to treat adverse events, atezolizumab may be held for >12 weeks after the last dose until corticosteroids are discontinued or reduced to prednisone dose of ≤ 10 mg/day (or equivalent).

Atezolizumab treatment may be suspended for reasons other than toxicity (e.g., surgical procedures). The acceptable length of treatment interruption must be based on an assessment of benefit–risk by the investigator and in alignment with the protocol requirements for the duration of treatment and documented by the investigator. The Medical Monitor is available to advise, as needed.

Guidelines for management of specific adverse events associated with atezolizumab are provided in the [Appendix 9](#).

5.2 SAFETY PARAMETERS AND DEFINITIONS

Safety assessments will consist of monitoring and recording adverse events, including serious adverse events and adverse events of special interest, performing protocol-specified safety laboratory assessments, measuring protocol-specified vital signs, and conducting other protocol-specified tests that are deemed critical to the safety evaluation of the study.

Certain types of events require immediate reporting to the Sponsor, as outlined in Section 5.4.

5.2.1 Adverse Events

According to the ICH guideline for Good Clinical Practice, an adverse event is any untoward medical occurrence in a clinical investigation subject administered a pharmaceutical product, regardless of causal attribution. An adverse event can therefore be any of the following:

- Any unfavorable and unintended sign (including an abnormal laboratory finding), symptom, or disease temporally associated with the use of a medicinal product, whether or not considered related to the medicinal product
- Any new disease or exacerbation of an existing disease (a worsening in the character, frequency, or severity of a known condition), except as described in Section 5.3.5.10
- Recurrence of an intermittent medical condition (e.g., headache) not present at baseline

- Any deterioration in a laboratory value or other clinical test (e.g., ECG, X-ray) that is associated with symptoms or leads to a change in atezolizumab treatment or concomitant treatment or discontinuation from study drug
- Adverse events that are related to a protocol-mandated intervention, including those that occur prior to assignment of atezolizumab treatment (e.g., screening invasive procedures such as biopsies)

5.2.2 Serious Adverse Events (Immediately Reportable to the Sponsor)

A serious adverse event is any adverse event that meets any of the following criteria:

- Is fatal (i.e., the adverse event actually causes or leads to death)
- Is life threatening (i.e., the adverse event, in the view of the investigator, places the patient at immediate risk of death)

This does not include any adverse event that had it occurred in a more severe form or was allowed to continue might have caused death.

- Requires or prolongs inpatient hospitalization (see Section [5.3.5.11](#))
- Results in persistent or significant disability/incapacity (i.e., the adverse event results in substantial disruption of the patient's ability to conduct normal life functions)
- Is a congenital anomaly/birth defect in a neonate/infant born to a mother exposed to study drug
- Is a significant medical event in the investigator's judgment (e.g., may jeopardize the patient or may require medical/surgical intervention to prevent one of the outcomes listed above)

The terms "severe" and "serious" are not synonymous. Severity refers to the intensity of an adverse event (e.g., rated as mild, moderate, or severe, or according to National Cancer Institute Common Terminology Criteria for Adverse Events [NCI CTCAE]; see Section [5.3.3](#)); the event itself may be of relatively minor medical significance (such as severe headache without any further findings).

Severity and seriousness need to be independently assessed for each adverse event recorded on the eCRF.

Serious adverse events are required to be reported by the investigator to the Sponsor immediately (i.e., no more than 24 hours after learning of the event; see Section [5.4.2](#) for reporting instructions).

5.2.3 Adverse Events of Special Interest (Immediately Reportable to the Sponsor)

See [Appendix 10](#) for list of adverse events of special interest.

5.3 METHODS AND TIMING FOR CAPTURING AND ASSESSING SAFETY PARAMETERS

The investigator is responsible for ensuring that all adverse events (see Section [5.2.1](#) for definition) are recorded on the Adverse Event eCRF and reported to the Sponsor in accordance with instructions provided in this section and in, Sections [5.4](#), [5.5](#), and [5.6](#).

For each adverse event recorded on the Adverse Event eCRF, the investigator will make an assessment of seriousness (see Section [5.2.2](#) for seriousness criteria), severity (see Section [5.3.3](#)), and causality (see Section [5.3.4](#)).

5.3.1 Adverse Event Reporting Period

Investigators will seek information on adverse events at each patient contact. All adverse events, (including the neoadjuvant phase, surgery phase, and adjuvant phase) whether reported by the patient or noted by study personnel, will be recorded in the patient's medical record and on the Adverse Event eCRF.

After informed consent has been obtained **but prior to initiation of study drug**, only serious adverse events caused by a protocol-mandated intervention (e.g., invasive procedures such as biopsies, discontinuation of medications) should be reported (see Section [5.4.2](#) for instructions for reporting serious adverse events).

After initiation of study drug, all adverse events will be reported until 30 days after the last dose of atezolizumab (neoadjuvant or adjuvant, whichever occurs last). Serious adverse events and non-serious adverse events of special interest will be reported until 90 days after the last dose of atezolizumab (neoadjuvant or adjuvant, whichever occurs last). For patients participating in the Adjuvant Atezolizumab Therapy Phase, as outlined in Section [3.1.4](#), who will receive and complete SOC chemotherapy prior to adjuvant atezolizumab, all AE's will be reported from their first dose of neoadjuvant atezolizumab until 30 days after the last dose of adjuvant atezolizumab. Additionally, serious adverse events and non-serious adverse events of special interest will be reported until 90 days after the last dose of adjuvant atezolizumab for these patients. During the Surveillance Period, as outlined in Section [3.1.3](#), if a patient is not receiving atezolizumab, only serious adverse events associated with CT scans, blood sample collection, and the optional biopsy (collected at the time of disease progression) will be collected and reported (see [Table 5](#)).

Table 5 Reporting Requirements After Initiation of Study Drug (by Treatment Subgroup)

Safety Reporting Requirements	Subgroup A	Subgroup B	Subgroup C	Subgroup D
No Adjuvant Treatment	Adjuvant Atezolizumab Treatment	SOC Chemotherapy (± Radiotherapy) only	SOC Chemotherapy (± Radiotherapy) plus Adjuvant Atezolizumab	
AEs	From first dose of neoadjuvant atezolizumab until 30 days after last dose of neoadjuvant atezolizumab ^b	From first dose of neoadjuvant atezolizumab until 30 days after last dose of adjuvant atezolizumab ^{a, b}	From first dose of neoadjuvant atezolizumab until 30 days after last dose of neoadjuvant atezolizumab ^b	From first dose of Neoadjuvant atezolizumab until 30 days after last dose of Adjuvant atezolizumab ^{a, b}
SAEs/AESIs	From first dose of neoadjuvant atezolizumab until 90 days after last dose of neoadjuvant atezolizumab ^{b, c}	From first dose of neoadjuvant atezolizumab until 90 days after last dose of adjuvant atezolizumab ^{a, b, c}	From first dose of neoadjuvant atezolizumab until 90 days after last dose of neoadjuvant atezolizumab ^{b, c}	From first dose of neoadjuvant atezolizumab until 90 days after last dose of adjuvant atezolizumab ^{a, b, c}

AE = adverse event; AESI = adverse event of special interest; SAE = serious adverse event;

SOC = standard of care.

- ^a No safety reporting interruption between neoadjuvant and adjuvant atezolizumab.
- ^b After informed consent has been obtained but prior to initiation of study drug, adverse events should be reported as outlined in Section 5.3.1. During Surveillance, but after patients have already completed atezolizumab treatment, AEs should be reported as outlined in Section 5.3.1.
- ^c Serious adverse events associated with CT scans, blood sample collection, and the optional biopsy (collected at the time of disease progression) will be collected and reported during the entire Surveillance period.

Instructions for reporting adverse events that occur after the adverse event reporting period are provided in Section 5.6.

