5.4.2.2 Events That Occur after Study Drug Initiation

After initiation of study drug, adverse events will be reported until 30 days after the last dose of atezolizumab (neoadjuvant or adjuvant, whichever occurs last). See [Table 5](#) for full details. Serious adverse events and adverse events of special interest will be reported until 90 days after the last dose of atezolizumab (neoadjuvant or adjuvant, whichever occurs last). Only serious adverse events associated with CT scans, blood sample collection, and optional biopsy at the time of disease progression/recurrence that occur after the 90 day reporting window, but during the Surveillance period, will be collected and reported (see [Table 5](#)). Investigators should record all case details that can be gathered immediately (i.e., within 24 hours after learning of the event) on the Adverse Event eCRF and submit the report via the electronic data capture (EDC) system. A report will be generated and sent to Safety Risk Management by the EDC system.

In the event that the EDC system is unavailable, the *paper Clinical Trial Adverse Event/Special Situations Form* provided to investigators should be completed and submitted to the Sponsor or its designee immediately (i.e., no more than 24 hours after learning of the event), either by faxing or by scanning and emailing the form using the fax number or email address provided to investigators. Once the EDC system is available, all information will need to be entered and submitted via the EDC system.

Instructions for reporting serious adverse events that occur >90 days after the last dose of atezolizumab are provided in Section [5.6](#).

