rr After informed consent has been obtained but prior to initiation of atezolizumab treatment, only serious adverse events caused by a protocol-mandated intervention should be reported. After initiation of atezolizumab treatment, adverse events will be reported until 30 days after the last dose of atezolizumab (neoadjuvant or adjuvant, whichever occurs last). Serious adverse events and adverse events of special interest will be reported until 90 days after the last dose of atezolizumab (neoadjuvant or adjuvant, whichever occurs last; see Section [5.3.1](#)). All adverse events associated with CT scans, blood sample collection, and the optional biopsy (collected at the time of disease progression/recurrence) that occur after the 90-day reporting window, but during the Surveillance period, will also be collected and reported. After the designated reporting period, the Sponsor should be notified if the investigator becomes aware of any serious adverse event that is believed to be related to prior atezolizumab treatment. The investigator should follow each adverse event until the event has resolved to baseline grade or better, the event is assessed as stable by the investigator, the patient is lost to follow-up, or the patient withdraws consent. Every effort should be made to follow all serious adverse events and adverse events of special interest considered to be related to atezolizumab treatment or trial-related procedures until a final outcome can be reported.

Appendix 2

Timing of Surveillance Assessments

The overall Schema for Surveillance Assessments is provided in [Figure 1](#).

Detailed timing of Surveillance assessments for each adjuvant treatment subgroup can be found in [Tables 1–4](#), as follows:

[Table 1](#) Group A – No Adjuvant Treatment

[Table 2](#) Group B – Adjuvant Atezolizumab Treatment

[Table 3](#) Group C – SOC Chemotherapy (\pm Radiotherapy) Only

[Table 4](#) Group D – SOC Chemotherapy (\pm Radiotherapy) + Adjuvant Atezolizumab Treatment

Appendix 2

Timing of Surveillance Assessments (cont.)

Figure 1: Surveillance Assessments Schema

Visit	Surveillance									Survival F/U
	Year 1			Year 2			Year 3+			
	6 wks	6 wks	3 mo	3 mo	3 mo	3 mo	3 mo	3 mo	3 mo	
Surveillance Baseline; Post-surgery	S1	S2	S3	S4	S5	S6	S7	S8	S9	
Extended Chest CT	+			+	+	+	+	+	+	+
Whole blood for serum/plasma	+	+	+	+	+	+	+	+	+	+
Whole blood for PBMCs	+				+					

S=Surveillance (Visit); PBMC=peripheral blood mononuclear cells.

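### For operated patients without adjuvant atezolizumab, required reporting of events that are neither serious nor AESI nominally ends 12 days after surgery, and the SAP's post-operative tables pool unequal reporting windows

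*Protocol*

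**What the plan says.** The 30-day limit stands in four places in the protocol. Section 5.3.1 states "all adverse events will be reported until 30 days after the last dose of atezolizumab (neoadjuvant or adjuvant, whichever occurs last". Section 5.4.2.2 repeats it: "After initiation of study drug, adverse events will be reported until 30 days after the last dose of atezolizumab". Table 5 gives the window for Subgroups A and C as "From first dose of neoadjuvant atezolizumab until 30 days after last dose of neoadjuvant atezolizumab". Appendix 1 note rr says the same and is copied into SAP Section 4. Serious events and adverse events of special interest (AESIs) run to 90 days after the last dose. For Subgroups B and D, Table 5 note a adds "No safety reporting interruption between neoadjuvant and adjuvant atezolizumab".

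Other text points the other way. Section 5.3.1 opens with an undated sentence on recording in the case report form: "All adverse events, (including the neoadjuvant phase, surgery phase, and adjuvant phase". Appendix 1 also marks adverse events at the Post-surgery Visit, although that row carries note rr. Note e lets the Treatment Discontinuation Visit of patients without adjuvant atezolizumab be held at the Post-surgery Visit, even when that is more than 30 days after the last dose.

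For procedures during Surveillance the text contradicts itself. Section 5.3.1 collects, "if a patient is not receiving atezolizumab, only serious adverse events associated with CT scans, blood sample collection, and the optional biopsy". Section 5.4.2.2 agrees: "Only serious adverse events associated with CT scans, blood sample collection, and optional biopsy at the time of disease progression/recurrence". Note rr collects more: "All adverse events associated with CT scans, blood sample collection, and the optional biopsy".

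SAP 6.4.1 plans summaries of events starting on or after the day of surgery, for everyone in the safety population who was operated on: Tables 14.3.1.2c (all events), 14.3.1.4b (treatment-related) and 14.3.1.5c (serious). All three are flagged for both interim analyses and the primary analysis. For patients who go on to adjuvant atezolizumab, events count to the day before the first adjuvant cycle. There is no common cut-off and no split by subgroup.

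**The concern.** Protocol 6.7.1.1 names the safety of lung resection after checkpoint inhibition as a question on which data are limited. The reporting window is tied to the last dose, not to the operation, so how much of the post-operative period is covered depends on the schedule and on whether adjuvant atezolizumab follows. The SAP then reports one percentage over patients whose windows differ several-fold.

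Some events in the gap matter. Section 5.1.1 lists hypothyroidism as a risk of atezolizumab, but the endocrine AESIs in Appendix 10 include hyperthyroidism and not hypothyroidism. Thyroid tests are due at the Post-surgery Visit. A non-serious hypothyroidism first found there in Subgroup A or C falls outside required reporting as written. Section 5.6 does not recover it, because that section covers only serious events and AESIs.

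**Working it through.** The plan states no figure for this point, so there is none to reproduce. The check is day arithmetic on the schedule.

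**Inputs.** Dose 2 on Day 22 and surgery on Day 40 (±10), from Appendix 1. The window for dose 2 is ±3 days in Appendix 1 and ±2 days in Section 4.3.2. The Post-surgery Visit is 4–6 weeks after surgery (Appendix 1). Surgery after one dose is allowed (4.6.2), and surgery may be delayed for an adverse event with no stated limit (Appendix 1 note j). If dose 2 is late, later visits move with it (note i). About 180 patients are enrolled and about 50 are expected to receive adjuvant atezolizumab (4.1). Any adjuvant treatment is recommended to start within 120 days of surgery, and atezolizumab within 60 days of the end of chemotherapy or radiotherapy (3.1.4).

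**Required all-event reporting after surgery in A and C** = last-dose day + 30 − surgery day:

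- Nominal: 22 + 30 − 40 = 12 days.
- Dose 2 on Day 22, surgery on Day 30 to 50: 22 down to 2 days. A late dose 2 moves surgery with it, so 22 stays the upper limit: 25 + 30 − 33 = 22.
- Early dose 2, surgery on Day 50: 20 + 30 − 50 = 0 (±2 window) or 19 + 30 − 50 = −1 (±3 window).
- One dose only, surgery on Day 40: 1 + 30 − 40 = −9 days.
- Surgery delayed for an adverse event: shorter still.

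**Distance to the Post-surgery Visit.** The visit falls on Day 40 + 28 = 68 to 40 + 42 = 82. Reporting closes on Day 52, so the visit comes 68 − 52 = 16 to 82 − 52 = 30 days later.

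**Serious events and AESIs.** Nominally 22 + 90 − 40 = 72 days after surgery. The first 28 days are not fully covered if surgery is after Day 22 + 90 − 28 = 84 (two doses) or Day 1 + 90 − 28 = 63 (one dose).

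**B and D in the same tables.** A B patient starting at the 120-day limit contributes 119 days, 119/12 = 9.9 times the nominal A/C window. With assumed starts at 28, 42 or 60 days, the windows are 27, 41 or 59 days (2.3, 3.4 or 4.9 times). D can run longer: up to 120 days, plus the length of chemotherapy (not given), plus up to 60 days.

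**Share of operated patients in A and C.** The operated fraction is not given. Assuming 60–100% of 180, with 50 receiving adjuvant atezolizumab: (108 − 50)/108 = 54% to (180 − 50)/180 = 72%.

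**Required capture over the first 28 post-operative days, in patient-days.** In A/C: 12/28 = 43% (2/28 = 7% to 22/28 = 79% for surgery on Days 30 to 50). Pooled, taking B and D as fully covered: 1 − 0.722 × 16/28 = 59% to 1 − 0.537 × 16/28 = 69%. For surgery on Days 30 to 50 the pooled range widens to 1 − 0.722 × 26/28 = 33% and 1 − 0.537 × 6/28 = 88%.

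Events cluster early, so the share of events captured may be higher. If the event rate halves every h days, the share of 28-day events falling in the first 12 days is (1 − 2^(−12/h))/(1 − 2^(−28/h)): 60% for h = 14 and 74% for h = 7, against 43% at a constant rate. The half-lives are assumptions.

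**Phase label in the SAP.** Section 3.1 uses Surveillance/Survival Follow-up Phase for adjuvant treatment, while 6.2.1 uses it for all Subgroups A to D. Section 6.4.1 dates events by that label, so the A/C end date is unclear. Neither reading gives A/C an earlier cut-off. Their cut-off comes only from the protocol's reporting period.

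**The case against.** The strongest reply is that the 30-day rule is not the only text. The undated sentence names the surgery phase, and the Post-surgery Visit is marked for adverse events. Section 4.5.4 sends new or worsened clinically significant findings at later visits to the adverse event form, and concomitant medications are collected to the Post-surgery Visit in patients without adjuvant atezolizumab (4.4). That visit is also the Surveillance baseline, so the narrower Surveillance rule need not apply before it. SAP 6.4.1 does not truncate at 30 days, so any event a site does record enters the tables. This stands: the documents show a shortfall in required capture, not a proven loss of data. But none of these texts gives a later end date, and four places give the earlier one. Sites that read them differently will capture differently.

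A second reply is that a drug-anchored window suits an objective about the safety of atezolizumab, and that the affected events are minor ones in descriptive, untested tables. Much of this stands too. Events that require or prolong hospitalization are serious, and pneumonitis and Grade 2 or higher cardiac disorders are AESIs. Later drug-related serious events and AESIs remain notifiable under Section 5.6. None of this removes the unequal windows within one percentage.

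The operated fraction, the figure of 50 and the event half-lives are assumed or approximate, so the pooled percentages show scale only.

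**Conclusion.** The point holds as a cheap improvement. As written, required reporting of events that are neither serious nor AESI nominally ends 12 days after surgery in Subgroups A and C, and earlier after one dose or delayed surgery. The SAP pools these patients with others whose window can be several times longer. If sites follow the 30-day rule, the incidence of lesser post-operative events is under-counted in A and C. Table 14.3.1.5c has a milder form of the same fault.

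A reader might infer that post-operative safety data are being lost across the board, or that the interim safety rule is compromised. The documents do not support either. The first depends on how sites read conflicting text. The second fails because Grade 5 events are serious and reported under the longer rule. A reader might equally infer that serious events and AESIs are always covered for the first 28 days; the calculation shows that they are not.

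The nominal figures rest only on the schedule and the written rule.

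**What to change.** 1. **Protocol.** Reconcile 5.3.1, Table 5, 5.4.2.2 and note rr (with its SAP copy) so that, for operated patients, all-event reporting runs to the later of 30 days after the last dose and the Post-surgery Visit. At the nominal schedule this raises required capture in A and C from 12 days to 28–42 days after surgery. In the same change, settle whether serious or all events linked to Surveillance procedures are collected, and the two Post-surgery Visit timings (4–6 weeks in Appendix 1; 30 ± 7 days in Appendix 3).
2. **SAP 6.4.1.** Keep the existing tables. Add either a version with a common post-operative onset window (for example surgery to 28 days after, stating how a first adjuvant dose inside it is handled) or a split by adjuvant atezolizumab yes/no. Define the phase label and the A/C end date. Report how many operated patients had a required reporting period shorter than the common window.

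The documents do not show whether all operations are done. If they are, only the second item applies.

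The cost is wording changes, a few more weeks of recording lesser events at a visit already scheduled and marked for adverse events, and a few extra tables. No existing table is lost.
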